#### 9.4.6 Additional Analysis for Primary Effectiveness Endpoint

Univariate and multivariate logistic regression models will be used to examine the impact of the covariates on the primary effectiveness endpoint. If the sites are not poolable, then study site and operators will be treated as random effects in the regression model. All covariates included in the analysis will consist of the following:

	Definition/ Variables	Note
Demographics	
 
Age
 
Gender
 
Ethnicity
 
Race
 
Study Site
 
	
 
Continuous variable (unit: year)
 
Male, Female
 
Hispanic/ Latino or not
 
Asian, Black, Caucasian, Other
 
Random Effect if sites not poolable
 

Medical History	
 
Diabetes
 
Hypertension
 
Structural heart disease
 
Atrial Flutter
 
Duration of AF history
 
Frequency of AF episodes
 
	
Cardiac Medical History	
 
Previously tried Class I AADs
 
Previously tried Class II AADs
 
Previously tried Class III AADs
 
Previously tried Class IV AADs
 
	
 
Class I: Disopyramide, Flecainide, Propafenone, Quinidine
 
Class II: (Beta-Blocker): Acebutolol, Atenolol, Metoprolol, Propranolol, Sotalol, and other Beta-Blocker
 
Class III: Amiodarone, Dofetilide
 
Class IV: Verapamil, Diltiazem
 

TTE Result	Baseline left atrial dimension	
Ablation Procedure	
 
Repeated ablation procedure or not
 
Procedure success
 
Use of Isoproterenol
 
Use of Adenosine
 
Agilis Sheath
 
Other Sheath
 
Total procedure time
 
CF values
 
Average power
 
Average impedance
 
Average temperature
 
Total RF ablation time
 
Tag index value
 
Etc.
 
	

The primary effectiveness endpoint will be the dependent variables and the covariates will be treated as independent variables. Univariate logistic regression models will be conducted for each of the potential predictors. A p-value <0.20 is to be used as the cut-off point for screening covariates. Forward model selection will be used to select predictors that remain significant at p-

value <0.05 in the multivariate model. Interaction terms may be examined based on those covariates that remain significant in the final model.

The analysis population of the additional analysis for the primary effectiveness endpoint will be the PP population. This analysis will only be performed after the 12 months follow-up is complete.

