#### 4. STUDY ENDPOINTS

#### **4.1 Primary Endpoints**

#### 4.1.1 Primary Effectiveness Endpoint

The primary effectiveness endpoint is defined as the freedom from documented (Symptomatic and asymptomatic) atrial fibrillation, atrial flutter and atrial tachycardia (AF/AFL/AT) (hereinafter collectively referred to as "atrial tachyarrhythmias") recurrence (episodes  $\geq$  30 secs on TTM or continuously recorded on the standard 12-leads ECG or 24 Hour Holter monitoring) during the evaluation period (Day 91-365) and freedom from the following failure modes:

- Acute procedural failure, including:
  - Failure to confirm entrance block in all pulmonary veins post-procedure,
- Repeat ablation failure, including:
  - $\circ$  > 1 repeat ablation procedures during the 3-Month Blanking Period (Day 0-90) after the index ablation procedure.
  - Any repeat ablation procedure during the Evaluation Period.
- DC cardioversion for AF/AFL/AT following the 3-month blanking period
- Surgical treatment for AF/AFL/AT after the index ablation procedure.
- AAD failure: Taking a new AAD, a previously failed AAD at a greater than the highest ineffective historical dose or starting an AAD for AF during the evaluation period (refer to section 5.14 for details).

In summary, effectiveness success is defined as freedom from atrial tachyarrhthmia during the Evaluation Period, off or on a previously failed AAD, and not exceeding 1 repeat ablation procedures for an atrial tachyarrhthmia during the 3-Month Blanking Period.

This study is designed to compare the primary effectiveness of the VISITAG SURPOINT™ Module with EPU to a pre-determined performance goal of 50%, which is indicated as the minimum acceptable success rate at 12 months for a paroxysmal AF population in the 2017 HRS/EHRA/ECAS/APHRS/SOLAECE consensus statement.

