#### 5. PRIMARY AND SECONDARY ENDPOINT(S) AND ASSOCIATED HYPOTHESES

#### 5.1 Primary Endpoints and Associated Hypotheses

#### 5.1.1 Primary Effectiveness Endpoint

The primary effectiveness endpoint of this study is the effectiveness success rate at Month 12, defined as the proportion of subjects who are freedom from documented (symptomatic and asymptomatic) atrial fibrillation, atrial flutter and atrial tachycardia (AF/AFL/AT) (hereinafter collectively referred to as "atrial tachyarrhythmias") recurrence (episodes  $\geq$  30 secs on TTM or continuously recorded on the standard 12-leads ECG or holter) during the evaluation period (Day 91-365) and freedom from the following failure modes:

- Acute procedural failure, including:
  - Failure to confirm entrance block in all pulmonary veins at the end of procedure
- Repeat ablation failure, including:
  - > 1 repeat ablation procedures during the 3-Month Blanking Period (Day 0-90) after the index ablation procedure.
  - o Any repeat ablation procedure during the evaluation period.
- DC cardioversion for AF/AFL/AT following the 3-month blanking period
- Surgical treatment for AF/AFL/AT after the index ablation procedure.
- AAD failure: Taking a new AAD for AF, a previously failed AAD at a greater than the highest ineffective historical dose during the evaluation period.

This study is designed to compare the primary effectiveness of the VISITAG SURPOINT Module with EPU to a pre-determined performance goal of 50%, which is indicated as the minimum acceptable success rate at 12 months for a paroxysmal AF population in the 2017 HRS/EHRA/ECAS/APHRS/SOLAECE consensus statement.

The final analyses for primary effectiveness endpoint will apply Bayesian methods and use a beta-binomial model .

The hypotheses to be tested for this evaluation are:

$$H_0: p \le 0.50$$
 vs.  $H_A: p > 0.50$ ,

where p is the effectiveness success rate

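### The SAP 9.4.6 predictor model includes an unwindowed repeat-ablation term that partly overlaps the outcome, and an undefined procedure-success term that, on its likeliest reading, is an outcome component

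*SAP*

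**What the plan says.** SAP 9.4.6 sets up univariate and multivariate logistic models: "The primary effectiveness endpoint will be the dependent variables and the covariates will be treated as independent variables". Under the ablation-procedure heading its covariate table lists "Repeated ablation procedure or not" and "Procedure success". The first has no time window or count, and the second is not defined there. Selection has two stages: "A p-value <0.20 is to be used as the cut-off point for screening covariates", then forward selection at p<0.05. The section does not name the test behind these p-values and gives no rule for sparse or empty cells. The model is fitted in the per-protocol population after 12-month follow-up is complete.

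SAP 5.1.1 defines the dependent variable. Three of its failure modes matter here:

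- "Failure to confirm entrance block in all pulmonary veins at the end of procedure"
- "> 1 repeat ablation procedures during the 3-Month Blanking Period (Day 0-90) after the index ablation procedure"
- "Any repeat ablation procedure during the evaluation period"

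Protocol 4.1.1 summarises success as, among other conditions, "not exceeding 1 repeat ablation procedures for an atrial tachyarrhthmia during the 3-Month Blanking Period". One blanking-period repeat is therefore compatible with success.

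SAP 9.4.5 also uses repeat procedure as a subgroup factor. There it is confined to the blanking period and carries a caution about confounding of post-baseline subgroups. SAP 9.4.6 has neither the restriction nor the caution.

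**The concern.** A covariate that is wholly or partly a component of the outcome will be associated with it whatever the biology. A reader of the final report could take such a coefficient as evidence that repeat ablation, or an incomplete index procedure, predicts failure, when it mostly restates how failure was defined. Such a term may also take a place in the forward-selected model, which examines Tag Index value and contact force in a study of Tag Index-guided ablation. A term with no finite estimate adds a practical problem: the software may fail, or return an uninterpretable coefficient.

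**Working it through.** **The plan's own figure.** SAP 9.4.6 states none. The nearest is the power of more than 90% in SAP 8, which reproduces under the fixed-sample decision rules of SAP 9.4.1 (interim looks not simulated). With 300 subjects, effectiveness needs at least 167 successes (type I error 0.028, power 0.9997) and safety allows at most 31 events (type I error 0.036, power 0.940). With 281 subjects (330 × 0.85 = 280.5), power is 0.999 and 0.934. The predictor model enters none of this.

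**Overlap, side by side.**

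| Subject | Outcome under SAP 5.1.1 | Covariate in SAP 9.4.6 |
|---|---|---|
| One blanking repeat | Success possible | Repeat = yes |
| Two or more blanking repeats | Failure by definition | Repeat = yes |
| Any evaluation-period repeat | Failure by definition | Repeat = yes |
| Entrance block not confirmed in all veins | Failure by definition | Procedure success = no, if so defined |

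**Repeat term.** Inputs: 65% overall success (SAP 8) and 300 subjects (330 less about 30). The documents give no repeat rates, so these are assumed and varied. Let b be the proportion with exactly one blanking repeat and e the proportion with an evaluation-period repeat. Assume no multiple blanking repeats, and that repeats are unrelated to every other failure mode.

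- Success among subjects not failed by a late repeat: s = 0.65/(1 − e)
- Success in the repeat group: r = b·s/(b + e)
- Odds ratio for success = [r/(1 − r)] / [s/(1 − s)]

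For b = e = 5%: s = 0.65/0.95 = 0.684; r = 0.05 × 0.684/0.10 = 0.342; OR = (0.342/0.658)/(0.684/0.316) = 0.520/2.167 = 0.24.

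For b = 7%, e = 3%: s = 0.65/0.97 = 0.670; r = 0.7 × 0.670 = 0.469; OR = 0.883/2.031 = 0.43.

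A simulation of 1,000 trials per scenario, using the likelihood-ratio test, gave:

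| Single blanking / late repeats | Median OR | p<0.20 | p<0.05 | No success among repeats |
|---|---|---|---|---|
| 5% / 5% | 0.24 | 98.9% | 94.9% | 0.1% |
| 7% / 3% | 0.43 | 79% | 57% | 0% |
| 1% / 8% | 0.04 | 100% | 100% | 12% |
| 0% / 8% | none | 100% | 100% | 100% |
| 5% / 0% (restricted covariate) | 1.00 | 20.8% | 5.9% | 0% |

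The last row is what a covariate with no effect should show. The association in the other rows comes from the endpoint definition alone. The estimate is nevertheless finite unless almost no repeat falls in the blanking period.

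**Procedure success.** Read it as entrance block in all veins at the end of the procedure. The cell for acute failure with endpoint success is then zero by definition. With no acute failures the covariate is constant. With one or more there is quasi-complete separation, and the maximum-likelihood estimate is infinite. For a acute failures among 300 subjects with 195 successes and 105 failures, the Fisher p-value is the product of (105 − i)/(300 − i) for i = 0 to a − 1:

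- a = 1: 105/300 = 0.35
- a = 2: 0.35 × 104/299 = 0.12
- a = 3: 0.1217 × 103/298 = 0.042
- a = 6: 0.0017
- a = 9: 0.00006

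An ordinary logistic fit stopped with a singular matrix at a = 3 and a = 6. At a = 9 it did not converge (log-odds ratio 21.3, standard error 9809), with a Wald p of 0.998 and a likelihood-ratio p of 0.00001. Whether the covariate passes the p<0.20 screen thus depends on the number of acute failures and on a test the SAP does not name.

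**The case against.** Four points can fairly be made for the plan.

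**Procedure success is undefined.** SAP 5.2.1 lists several measures under acute procedural success, including block after first encirclement, which is not an outcome component. On that reading there is no separation. This stands, and it makes the separation result conditional. Protocol 5.10 does tie acute success to isolation of all veins, which favours the problematic reading.

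**The repeat term may be meant as in SAP 9.4.5.** If only blanking-period repeats count, the overlap shrinks to subjects with more than one. With 5% single and 0.5% multiple repeats assumed, the median odds ratio is 0.78, with p<0.05 in 9% of trials. The problem is then small, but SAP 9.4.6 does not state that restriction.

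**Acute failures may be few.** Protocol 5.11 calls for further ablation and rechecking when conduction returns. A reader might infer that both terms will pass the screen and be selected first. The documents do not support that: for procedure success, zero or one acute failure, or a Wald test, would keep it out.

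**Distortion of other coefficients is not established.** A reader might infer that the Tag Index and contact-force estimates will be materially biased. In one assumed scenario (800 trials; true log-odds ratio 0.4 per SD for recurrence; 24% of recurrences re-ablated late at random; 4% blanking repeats; 2% acute failures), the mean coefficient for success was −0.395 without the terms, −0.394 with the repeat term and −0.413 with procedure success. Detection at p<0.05 fell from 88% to 83% with the repeat term. The distortion could be larger if the decision to repeat depends on the predictor, but nothing in the documents allows that to be sized.

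A reader might also infer that both terms cause separation. The repeat term normally does not, because a single blanking repeat leaves success possible.

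**Conclusion.** The point holds in limited form. As written, the repeat covariate partly overlaps the outcome and carries an association built in by definition. With no real effect, the median odds ratio ranges from about 0.04 to 0.43 over the assumed mixes of blanking and late repeats that allow a finite estimate. Those rates are assumptions, as is independence of repeats from other failure modes. Procedure success is uninformative (constant or inestimable) if it means entrance block in all veins at the end of the procedure; the SAP needs to say what it means. Distortion of the other coefficients is possible but its size in this trial is unknown.

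The consequence is confined to an exploratory model fitted after follow-up ends. The Bayesian success rule, the interim analyses, power and sample size do not depend on it. The change should still be made, because it is cheap and the model would otherwise report associations that are true by construction.

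**What to change.** In the SAP 9.4.6 covariate table:

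1. Delete the procedure-success covariate, or replace it with a defined measure that is not an outcome component, such as entrance block after first encirclement.
2. Drop the repeat-ablation covariate, or limit it to a single repeat within the blanking period. SAP 9.4.5 already uses a blanking-period window; the limit to one repeat is needed because more than one is itself a failure. If the covariate is kept, carry over the SAP 9.4.5 caution about post-baseline variables.
3. Optionally, name the test used for screening and a method for sparse cells, such as Firth or exact logistic regression.

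The cost is a short SAP text edit. No new data are needed, and the primary analyses do not change.

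### SAP 9.4.6 calls covariates significant predictors after screening and forward selection on the same data, so it would often name a predictor of success when none exists

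*SAP*

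**What the plan says.** SAP 9.4.6 states its aim: "Univariate and multivariate logistic regression models will be used to examine the impact of the covariates on the primary effectiveness endpoint". The candidates are introduced with "All covariates included in the analysis will consist of the following", and a table follows. The table names 5 demographic items (one is study site), 6 medical-history items, 4 antiarrhythmic drug classes, 1 echocardiographic measure and 13 procedural items. That is 29, or 28 without study site. The procedural block includes Tag Index value, contact force, average power and total RF time, and it ends in 'Etc.'.

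The selection rule has three steps:
- Each covariate gets its own logistic model, and "A p-value <0.20 is to be used as the cut-off point for screening covariates".
- For the covariates that pass this screen, the plan continues: "Forward model selection will be used to select predictors that remain significant at" the level given as "value <0.05 in the multivariate model".
- On going further with the survivors, it adds: "Interaction terms may be examined based on those covariates that remain significant in the final model".

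On clustering: "If the sites are not poolable, then study site and operators will be treated as random effects in the regression model". On timing: "This analysis will only be performed after the 12 months follow-up is complete". The population is the per-protocol set.

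No other section limits how the results may be read. The 5% error control in SAP 6 and 9.4.1 is for the primary endpoints. The statements in SAP 5.2, 5.3, 9.5 and 9.6 that no formal inference will be done concern secondary and additional endpoints, whereas this regression models the primary one. The caution in SAP 9.4.5 is about confounding in subgroup comparisons. Protocol 7.9.5 only refers to the SAP.

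**The concern.** A covariate that has won a search over 28 candidates cannot be judged by an ordinary p<0.05, because the data that picked it are the data that test it. The rule nevertheless describes what it keeps as significant and does not tell the reader that the p-value ignores the search. The open end of the list and the optional interactions add choices that can be made after outcomes are known; SAP 3 says that the sponsor is not blinded to individual or aggregated data.

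What is at stake is the reliability of any predictor statement in the final report. A statement that Tag Index value or contact force predicts 12-month success would attract attention, and this procedure can produce one by chance.

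**Working it through.** **The plan's own figures.** The documents give no false-positive rate for SAP 9.4.6. The nearest stated figure is the power claim in SAP 8: more than 90% for each primary endpoint with 330 enrolled and 10-15% attrition. That leaves 330 × 0.85 = 280.5 to 330 × 0.90 = 297 subjects. A single final look under the rules in SAP 9.4.1 gives at least 99.9% power for effectiveness and 93.4-94.7% for safety at n = 281-297. The claim reproduces, and the sample size can be used below.

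**Inputs.**
- Candidates: 5 + 6 + 4 + 1 + 13 = 29, or 28 without study site (table in SAP 9.4.6).
- Screen p<0.20, forward entry p<0.05 (SAP 9.4.6).
- Success rate 65% (SAP 8); n about 300.
- Correlation among covariates: not in the documents. Assumed 0 to 0.7.

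**Information available.** At 65% success and n = 297, failures = 297 × 0.35 ≈ 104. Per candidate: 104 / 28 ≈ 3.7.

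**The screen gives no protection.** A covariate with univariate p<0.05 has already passed p<0.20, and the first forward step takes the smallest p-value. With the same test at both stages, the chance of keeping at least one covariate is therefore the chance that the smallest of the 28 univariate p-values is below 0.05.

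**Independent covariates, none related to outcome.**
- P(at least one kept) = 1 − 0.95^28 = 76.2%.
- With 29 candidates: 1 − 0.95^29 = 77.4%.

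**Correlated covariates, by simulation.** The full procedure was run with n = 300, 65% success, 28 single-parameter covariates (16 binary, 12 continuous), likelihood-ratio tests and 1,000 null trials per row.

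| Correlation structure | At least one kept | Mean number kept |
|---|---|---|
| 0 | 76.5% | 1.50 |
| 0.3, common | 73.4% | 1.31 |
| 0.5, common | 60.7% | 0.91 |
| 0.7, common | 51.7% | 0.64 |
| 0.5, blocks of 4 | 74.5% | 1.28 |
| 0.7, blocks of 4 | 69.5% | 1.13 |
| 0.5, blocks of 7 | 70.3% | 1.15 |

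About 5.7-6.1 null covariates passed the screen per trial. A separate simulation with Wald tests, n = 297 and 700 trials per setting gave 74% at correlation 0 and 57% at 0.5 for 28 covariates. With only 20 covariates at correlation 0.5 it gave 50%.

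**Two covariates that cannot be null.** 'Procedure success' and 'Repeated ablation procedure or not' overlap failure modes in the endpoint definition (SAP 5.1.1), so they are tied to the outcome by construction. Without them, 26 independent candidates give 1 − 0.95^26 = 73.7%.

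**The case against.** The strongest reply is that nothing in the trial turns on this regression. It is headed an additional analysis, runs after follow-up is complete, and enters neither the success rule in SAP 9.4.1 nor the interim rule in SAP 9.4.2. Its wording is partly tentative, and the SAP promises 5% control only for the primary endpoints. All of that stands, and it limits the weight of the point.

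A reader might infer more than the documents support in four ways:
- *That the trial's type I error is inflated.* It is not, for the reason just given.
- *That a 5% guarantee is exceeded many times over.* The 0.05 in SAP 9.4.6 is an entry threshold for each variable, not an error rate quoted for the whole search. Setting 50-76% against it compares unlike quantities.
- *That the reported confidence intervals will be too narrow.* SAP 9.4.6 does not promise intervals.
- *That a false predictor would corrupt the answer on Tag Index-guided ablation.* The trial compares one arm with performance goals of 50% and 14%. An association within that arm does not answer the trial's question, and the SAP does not say that it would.

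It is also fair to say that a complete null is a benchmark only, since at least two covariates are related to the endpoint by definition. Removing them barely changes the result. The objection therefore reduces the consequence but does not remove the defect: the rule still labels as significant what the search happened to find.

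**Conclusion.** The point holds as a limited one. Applied as written to covariates unrelated to outcome, SAP 9.4.6 would report at least one predictor in about 50-76% of trials. The upper end is exact arithmetic for 28 independent covariates. The lower end rests on an assumed common correlation as high as 0.7. Correlation confined to blocks, in the settings run, gives about 70-75%. The figures treat each covariate as a single parameter and leave out interactions and anything added under 'Etc.'; those could only add opportunities for chance findings. The primary success decision is untouched. The consequence is that predictor statements from this section, including any on Tag Index value or contact force, would not be reliable as worded.

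**What to change.** Change SAP 9.4.6 as follows:

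1. Delete 'Etc.' and fix the candidate list before the 12-month analysis. While doing so, decide how to treat the two covariates that overlap the endpoint's failure modes.
2. State that the regression is exploratory and that post-selection p-values will not be used to call a covariate statistically significant.
3. Report the univariate odds ratio of every candidate. Show the forward-selected model as a description, with each covariate's bootstrap selection frequency obtained by repeating the whole screening and selection procedure in each resample.

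A Holm adjustment across the closed list can be optional but should not be required. Its first step is 0.05 / 28 = 0.0018, where a covariate with 80% power at 0.05 would have about 37% (normal approximation), and it would rest the claim on unadjusted odds ratios.

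The cost is SAP wording, a short bootstrap on data already collected, and giving up the phrase 'significant predictor'. No new data are needed.

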#### 9.5 Analysis of Secondary Endpoints

No formal statistical hypothesis and inferential statistics will be formulated and performed for the secondary effectiveness and safety endpoints. Descriptive statistics including number and percentages of subjects/targets will be presented for each secondary endpoints. The number of events will also be presented. Secondary safety endpoints will be analyzed in the safety population. Secondary effectiveness endpoints will be analyzed in Full Set Effectiveness population.

